1.1 BACKGROUND

Preterm birth (birth before 37 weeks) is the major cause of neonatal mortality and morbidity in the United Kingdom (UK). Around 7% of UK babies are born preterm. Survival to age one year and rates of disability are inversely proportional to gestational length. Babies born at lower gestational ages do worse than those born at higher gestational ages. Importantly, although survival rates have increased with time, rates of disability remain unchanged (Costeloe, Hennessy et al. 2012, Moore, Hennessy et al. 2012).

There is uncertainty about the optimal method of delivery for preterm babies, as highlighted by NICE (Excellence 2015) and a Cochrane review (Alfirevic, Milan et al. 2013). Addressing this clinical uncertainty could significantly improve the Rates of intrapartum stillbirth, neonatal and long term mortality and morbidity which are higher in the 50,000 preterm babies born in the UK each year compared with term babies. It is plausible that planned delivery by caesarean Section (CS) could reduce either death or disability in preterm babies. Indeed, our recent retrospective study of 1575 UK babies born between 23 and 27 weeks gestation showed that, after adjusting for confounders, babies born vaginally had a higher odds (1.61 [95% Cl 1.01 – 2.58]) of intraventricular haemorrhage (Gamaleldin, Harding et al. 2017). Another study has shown that neonatal mortality is lower babies born by CS (Riskin, Riskin-Mashiah et al. 2008). Conversely, CS is associated with higher National Health Service (NHS) costs and greater complications for the mother (Excellence 2011) and there is conflicting evidence of benefit for preterm babies (Werner, Savitz et al. 2012, Alfirevic, Milan et al. 2013, Werner, Han et al. 2013).

Despite the lack of evidence and uncertainty in the national guidance, it is not clear whether clinicians and pregnant women are in equipoise about the best mode of delivery for preterm pregnant women and babies, nor whether they would wish to participate in any future randomised trial. Randomised trials have been performed to address optimal mode of delivery for women with breech presentation [(Hannah, Hannah et al. 2000) and women with twin pregnancy (Barrett, Hannah et al. 2013), and these trials have (arguably) reduced uncertainty. However, there are few randomised trials to compare planned CS with vaginal delivery for women with a cephalic presentation at term (Dodd, Crowther et al. 2013), and none registered for preterm gestations.

1.2 RATIONALE FOR STUDY

This study is a commissioned call from the Health Technology Assessment (HTA) because the National Institute for Clinical Excellence (NICE) guideline development group on preterm labour and birth were (in November 2015) were unable to find evidence to address the question: "For women who present in suspected or diagnosed preterm labour (who have not planned antenatally to give birth by caesarean section (CS) and for whom there are no other known indications for CS birth), what is the clinical effectiveness of deciding to carry out a CS compared with deciding to allow vaginal birth?" (Excellence 2015).

The HTA have also prioritised the research question, but are uncertain where evidence is really needed and whether women and clinicians would support randomisation. The aim of this study is to identify with more precision the clinical uncertainties among clinicians and women, any additional information possible (e.g. from new publications), and find out whether women and staff (and if so, under what clinical circumstances) would be willing to participate in a randomised trial. Designing a randomised trial is integral to addressing these issues.

The majority of preterm births follow the premature initiation of spontaneous labour. There is clinical uncertainty and little evidence about the optimal mode of delivery in this scenario or for those with planned preterm delivery. A minority require caesarean section (CS) (e.g. those with fulminating pre-eclampsia), and they are not the focus of this study. For the remainder, some clinicians believe that delivery by CS is best, due to the hypothesised reduction in birth trauma and intrapartum hypoxia. Others believe that vaginal delivery confers advantages for the baby (reducing respiratory morbidity), the mother (avoiding operative complications) and the NHS (costs).

There is only one systematic review of randomised trials on this topic, which is inconclusive (Alfirevic, Milan et al. 2013). Recent large cohort studies have not resolved this uncertainty, with evidence of worse outcomes (Werner, Savitz et al. 2012, Werner, Han et al. 2013) better outcomes (Reddy, Zhang et al. 2012) (Gamaleldin, Harding et al. 2017) and no difference (Kuper, Sievert et al. 2017) in association with CS. Not only is there uncertainty about mode of delivery, there is also uncertainty about clinician and women's willingness to participate in a randomised trial of method of delivery for preterm babies. In fact, the authors were unable to identify any research on women's willingness to participate in such a trial: indeed the only evaluation of willingness to participate in a 'method of delivery" trial is in twin pregnancy, where around 50% of women indicated they would be prepared to be randomised (McLeod, Barrett et al. 2004). A large trial was subsequently conducted, successfully addressing a major clinical

uncertainty (Barrett, Hannah et al. 2013). Importantly, in a study of term women with a previous CS, the majority were allocated by patient preference rather than randomisation to elective repeat CS or trial of vaginal delivery, suggesting reluctance to randomise or be randomised (Crowther, Dodd et al. 2012).

As we embark on the project, we will update the literature review for the NICE guideline (from November 2015) using the MeSH headings premature birth; delivery, obstetric OR caesarean delivery; labor, obstetric; in the time interval current date to five years previously. The purpose of this literature review is to determine the populations of preterm babies and the clinical scenarios where there is clinical uncertainty about the mode of delivery, and not to determine the feasibility of recruitment to a randomised trial.

We believe that this project will identify clinical uncertainties about the mode of preterm birth among clinicians and parents. It will also determine in which subgroups of women there is clinical uncertainty and who would be willing to undergo randomisation to either the intervention (caesarean section) or control (vaginal delivery). We will identify clinician willingness to recruit. We will also design (and provide approximate costs for) a randomised trial to address these clinical uncertainties in other words that it is the 'definitive' trial. Additionally, such a trial will only be worthwhile if it can be completed. If women (and clinicians) reject randomisation, the funds involved in commissioning a trial will be wasted.

If such a trial is feasible, and is commissioned, it could make an important impact on the outcome of babies being born preterm. A recent UK multicentre retrospective cohort study showed that the odds of severe intraventricular haemorrhage was 1.6 fold higher in babies of 23-32 weeks gestation born vaginally compared to those born by caesarean section (Gamaleldin, Harding et al. 2017). The potential impact of this on a UK population of babies being born between 23 and 32 weeks gestation can be calculated, based on around 2500 such UK births annually (Moser and Hilder 2008) a background prevalence of vaginal delivery of 40% (Gamaleldin, Harding et al. 2017), and a risk of around 25% of developing cerebral palsy for babies with severe intraventricular haemorrhage (Brouwer, Groenendaal et al. 2008). A very rough calculation suggests that if all babies between 23 and 32 weeks born by caesarean section, there would be 39 fewer cases of severe intraventricular haemorrhage and around ten fewer babies with cerebral palsy each year. These estimates should be viewed with extreme caution, given the assumptions made and the relatively wide confidence intervals. They also have to be set against the additional costs of caesarean section, and the adverse effects on maternal health (including the increased risk of stillbirth in a future pregnancy in association with caesarean section).

2 STUDY OBJECTIVES

2.1 OBJECTIVES

2.1.1 Primary Objective

This research aims to find out the groups of women and babies in preterm labour or with planned preterm delivery in whom is there clinical uncertainty about the optimal planned mode of birth and whether women and clinical staff would be willing to participate in a future randomised trial.

2.1.2. Secondary Objectives

To perform a survey with clinicians to establish CURRENT PRACTICE and OPINION in key clinical scenarios of women presenting in preterm labour (e.g. cephalic/breech, previous CS or not, indicated delivery for pre-eclampsia or not, twin pregnancy or not, 23, 26, 32 weeks gestation).

To CONVENE AN INTERACTIVE WORKING GROUP of clinicians, parents and other interested parties (including policy makers) to determine what kinds of trial/trials still need to be done, and what groups of women should be included. Formal consensus methodology will be used to resolve uncertainties.

To DESIGN A RANDOMISED TRIAL which addresses the agreed most important clinical uncertainties. In line with the HTA brief, we anticipate that the "control" in our randomised trial will be planned vaginal birth and the "intervention" will be planned CS, but this will be informed by the survey.

To mock up a SHORT TRIAL PROTOCOL to facilitate the qualitative study described below.

To perform a qualitative study among clinicians and women to determine the acceptability of randomization. We will conduct telephone interviews with clinicians, and focus groups with women who have had, or who are at risk of preterm birth.

Assuming that there are clinical uncertainties which can be addressed by a trial to which women and clinicians will support recruitment, we will finalise the design (and approximate costs) of a randomised trial of CS compared with vaginal delivery, to determine the optimal mode of delivery of women presenting in preterm labour

3.1.1 Primary Endpoint

Using surveys, focus groups, consensus workshops and interviews to identify and resolve clinical uncertainties about the willingness of clinicians and women to recruit to/participate in a trial about the best planned mode of birth for groups of women presenting in preterm labour or with planned preterm birth.

3.1.2 Secondary Endpoints

Survey results, working group report and consensus statement, protocol for randomised trial, and reports from qualitative studies.

4 STUDY DESIGN

The study design involves a survey of current practice and opinion, followed by an interactive consensus workshop and consensus study, followed by qualitative studies of women's and clinician views (focus groups, interviews), with each component informing the development of the next.

5 STUDY PLAN

5.1 Phase 1: Survey of current practice (Months 1-4)

We will perform a survey of clinicians regarding current practice and opinion offering examples of key clinical scenarios of women presenting in preterm labour or undergoing planned preterm delivery. The purpose of this survey is to determine the opinions of clinicians (consultant obstetricians, consultant neonatologists and midwives working in units with neonatal intensive care facilities) on the optimal mode of delivery. The survey will focus on scenarios where there is maximum clinical uncertainty and will be piloted to determine completion rates, ease of completion, and identify any questions which are unclear to respondents.

We will use a standardised format (likely an electronic format on a tool such as Bristol Online survey), and present options in the form of tick boxes and/or ratings scales. We will be careful to vary our "agree" or "highest rating score" between caesarean section and vaginal delivery to avoid bias from "yeasayers" (Boynton and Greenhalgh 2004). We believe that a closed ended design is likely to be appropriate, but we will include a free text box for further

communication at the end of the questionnaire. If comments in the free text box suggest there are important controversies that we have not presented, we will consider issuing a further survey. A request for demographic information of the respondent (age band, clinical specialty, preterm birth specialist or not) will be included at the end of the survey.

The survey will be distributed through our professional networks of contacts. Contacts will include clinicians participating in existing preterm birth intervention studies currently led by co-applicants involved in this study. We will also invite participation through the NHS Preterm Birth Network and Royal College of Obstetrician and Gynaecologists (RCOG) Preterm Birth Clinical Study Group (CSG). We will also advertise the survey through the Royal College of Obstetricians, the Royal College of Midwives, the British Maternal and Fetal Medicine Society, the British Association of Perinatal Medicine, the Neonatal Society. At the end of the survey we will ask participating clinicians if they would be willing to be contacted to take part in an interview for Phase 3, and for their consent for us to collect and keep their contact details for this purpose. We have attached a draft advert and a cover letter in which we invite clinicians to participate in the survey.

We acknowledge that where surveys are distributed through external organisations it will be difficult to determine the proportion of people completing the survey. However, we will aim for completion from around 200 individuals with good representation from each group of clinicians (obstetricians, neonatologists, midwives): we anticipate that this large and diverse sample will overcome any potential bias due to clustering of responses from any particular professional group.

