6.2 INCLUSION CRITERIA

Phase 1 surveys, we will include consultant obstetricians, neonatologists, and midwives working in hospitals with neonatal intensive care units (as these are the only hospitals that will

deliver the extreme preterm births, which are included in the scenarios). We will also include members of the public recruited via partner organisations and Public Patient Involvement (PPI) group, PICTR (Patient involvement in Clinical trials research). This is a group of i volunteers who are interested in supporting and commenting on research projects. The Centre for Reproductive Health (Edinburgh) Clinical Obstetric Trial team manages the PICTR group.

Phase 2 consensus workshop, we will recruit clinicians (obstetricians, anaesthetists, midwives, nurses and neonatologists and midwives) with 5 years of more experience or providing clinical care to women at risk of preterm labour or preterm infants born.

For the consensus workshops and Delphi process we will include women and their partners who fulfill the following criteria:

- age greater than 16 years
- willing to consent
- previous experience of the following
 - i. Previous preterm labour or delivery
 - ii. Women at risk of future preterm labour or delivery

Phase 3 Qualitative interviews we will recruit clinicians (obstetricians, anaesthetists, midwives, nurses and neonatologists and midwives) with 5 years of more experience or providing clinical care to women at risk of preterm labour or preterm infants born using volunteers from phase 1 and 2.

For the focus groups, we will recruit women only who fulfill the following criteria:

- age greater than 16 years
- willing to consent
- previous experience of the following
 - i. Previous preterm labour or delivery
 - ii. Women at risk of future preterm labour or delivery

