6.3 EXCLUSION CRITERIA

Phase 1, the survey

• We will exclude clinicians working in units without neonatal intensive care facilities

NB: Women and their partners who have experienced adverse events as a result of the issues

CASSAVA Version number 2 15th October 2018 IRAS ID 251310 above (e.g. neonatal death, stillbirth) will not be actively excluded from the consensus workshops or focus groups, but we will be mindful of the need to manage this sensitively. The members of the research team have significant experience of conducting mixed-methods research with parents who have experienced adverse events, including perinatal death.

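### The clinician survey is limited to staff of hospitals with neonatal intensive care, and to consultants among the doctors, but its listed respondent items record neither, so eligibility cannot be verified for most respondents.

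*Protocol*

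**What the plan says.** Protocol section 5.1 gives the survey's target group as "consultant obstetricians, consultant neonatologists and midwives working in units with neonatal intensive care facilities". Section 6.2 repeats the hospital condition and begins to give its reason: "midwives working in hospitals with neonatal intensive care units (as these are the only hospitals that will". Section 6.3 states it again as the only Phase 1 exclusion: "We will exclude clinicians working in units without neonatal intensive care facilities". The condition applies to clinicians only. A separate public survey has no such restriction: "We will also include members of the public recruited via partner organisations and Public Patient Involvement (PPI) group" (section 6.2).

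On what respondents are asked about themselves, section 5.1 says: "demographic information of the respondent (age band, clinical specialty, preterm birth specialist or not) will be included at the end of the survey". The bracketed list is not introduced as a set of examples.

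On distribution, section 5.1 names professional contacts and networks and adds: "We will also advertise the survey through the Royal College of Obstetricians, the Royal College of Midwives", followed by several specialist societies. Section 9.2 describes direct email and circulation through network and society lists. Section 11 states that the surveys gather no personal data, IP addresses included, except from people who volunteer their contact details.

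Section 13.2 then sorts each scenario by the percentage of respondents who agree: above 85%, 70-85%, 50-70% and below 50%.

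**The concern.** An eligibility rule works only if someone can tell who meets it. Here the rule depends on two facts about the respondent, the type of hospital and (for doctors) the grade, and neither is among the items listed. The distribution channels do not supply them, because nothing in the protocol says that college or society members all work in hospitals with neonatal intensive care, or that the doctors among them are all consultants. An anonymous return cannot be traced back to establish either fact.

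At stake are the agreement percentages. They decide whether a scenario is called accepted practice or uncertain, and the survey's list of uncertainties is what the Delphi exercise in section 5.2 starts from. If answers from outside the intended group are mixed in, the percentages describe a different population from the one the protocol defines. No later analysis plan can repair this, since a field that was never collected cannot be recovered.

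**Working it through.** **Step 1: set the requirements against the data.**

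| Eligibility condition | Where required | Listed respondent item that records it | Other route in the protocol |
|---|---|---|---|
| Hospital or unit has neonatal intensive care | 5.1, 6.2, 6.3 | None | Address, from volunteers only (11) |
| Consultant grade (doctors) | 5.1 | None | None stated |
| Profession | 5.1, 6.2 | Clinical specialty | Not needed |

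Only profession can be read from the answers. No screening question is described. By contrast, the Delphi in section 5.2 has participants register and give demographic details, and these are reviewed before an identifier is issued. The survey has no comparable step.

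**Step 2: what the possible effect looks like.** The protocol gives no figure for ineligible respondents, so there is nothing to reproduce. For scale, let q be the share of respondents who are ineligible and g the gap in agreement between eligible and ineligible respondents. Then

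observed agreement = (1 − q) × eligible agreement + q × ineligible agreement,

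so the shift is q × g. Both q and g are assumptions. The clinician survey size, 200, is from section 13.1.

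| q | Eligible n of 200 | Shift, g = 10 points | Shift, g = 20 points | Shift, g = 30 points |
|---|---|---|---|---|
| 5% | 190 | 0.5 | 1.0 | 1.5 |
| 10% | 180 | 1.0 | 2.0 | 3.0 |
| 20% | 160 | 2.0 | 4.0 | 6.0 |
| 40% | 120 | 4.0 | 8.0 | 12.0 |

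**Step 3: can a shift of that size change a label?** Suppose 88% of eligible and 68% of ineligible respondents agree (g = 20 points):

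- q = 10%: 0.90 × 88 + 0.10 × 68 = 86%, still above 85%.
- q = 20%: 0.80 × 88 + 0.20 × 68 = 84%, now in the 70-85% band.
- q = 30%: 0.70 × 88 + 0.30 × 68 = 82%, also in the 70-85% band.

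The label changes once q reaches (88 − 85)/20 = 15%. The direction could equally be the reverse if ineligible respondents agree more.

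**Step 4: compare with sampling error.** At 85% agreement and n = 200, the 95% half-width is 1.96 × √(0.85 × 0.15/200) = 4.9 points. The shift can match or exceed this when q and g are both large, and is well below it when either is small. Unlike sampling error, it does not shrink with more respondents.

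**The case against.** The strongest reply is that the protocol does not show every survey document. Section 5.1 refers to an attached advert and cover letter that are not at hand. They may state who is eligible, and self-selection on a stated rule is a normal way to apply a criterion in an anonymous survey. The questionnaire is still to be piloted, and a screening question need not count as a demographic item. People who volunteer an address could be checked. The survey is descriptive, a two-round Delphi and a consensus meeting follow it, and Delphi participants can add scenarios in round one.

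Much of this stands. A reader might infer that the exclusion cannot be applied at all; the documents do not support that, because self-selection is possible. They support only that no means of screening or verification is described for most respondents. Self-selection leaves no record, so its success could not be shown. The Delphi softens the consequence of a wrong label but does not correct the percentage that is reported.

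Two further readings are tempting and should not be pressed:

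- **Partial responders.** Because the respondent items come last, a reader might infer that people who stop early will be analysed without a known profession. Section 5.1 sets its target in completed surveys and section 9.2 infers consent from completion; nothing says partial returns will be used.
- **Later gestations.** The stated reason for the restriction is that only these hospitals "deliver the extreme preterm births, which are included in the scenarios", while section 2.1.2 gives as examples "twin pregnancy or not, 23, 26, 32 weeks gestation". A reader might infer that the restriction is mistaken for 32 weeks. Section 6.2 says only that extreme preterm births are among the scenarios, and using one clinician population throughout is a legitimate design choice.

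**Conclusion.** The point holds as a verification gap. The clinician survey's only exclusion, and its grade requirement for doctors, rest on facts that are not among the listed respondent items, in a survey that is otherwise anonymous and circulated through professional bodies. Ineligible answers may enter the section 13.2 percentages and, if they do, could not be identified and removed for most respondents.

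The size is not known. A shift of 2-8 points assumes an ineligible share of 10-40% and a 20-point gap; neither figure comes from the protocol. Over the wider grid above the range is 0.5 to 12 points. A scenario near a cut-off could be relabelled; one in the middle of a band probably would not be. The criterion should be read as working in a hospital that has neonatal intensive care, not as working inside the neonatal unit, and it does not touch the public survey. It would go too far to say that ineligible answers will certainly enter, or that the survey's conclusions are unsound. The change is worth making because it must be made before launch and costs almost nothing.

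**What to change.** In section 5.1, add two tick-box items to the clinician survey: whether the respondent's hospital has neonatal intensive care facilities (yes/no), and grade. Place them at the start, as screening questions, if the survey tool allows. Asking them at the end would still permit exclusion at analysis.

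In section 13.2, state that answers from clinicians who do not meet the section 5.1 and 6.3 conditions are left out of the agreement percentages, and that respondents with either item missing are counted and reported separately.

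The cost is two extra items and a sentence or two of text, which can go into the planned pilot. Neither item identifies anyone, so the undertaking in section 11 not to collect personal data is unaffected. After the survey has closed, the information could not be obtained for anonymous respondents.
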